**Figure 1: Study Design for KPL-301-C203**

A Safety Review Committee (SRC) including 2 physicians from the Sponsor, 1 physician from the Sponsor's contract research organization (CRO), and 1 independent physician who is an expert in critical care medicine, pulmonary disorders, infectious diseases and/or COVID-19 treatment (SRC Chairperson) will meet periodically to review AEs/SAEs, reasons for study discontinuations, and key clinical and laboratory assessments. SRC activities will be guided by an SRC Charter. The initial SRC meeting will be triggered once the initial 4 subjects have completed Day 8. SRC members will be blinded to subject treatment assignment.

A Data Monitoring Committee (DMC) has been established by the Sponsor to conduct periodic reviews and may meet more frequently as needed to review unblinded safety data from the Phase 2 and 3 portions of the study. The initial meeting will be triggered at 1 month after the first subject is enrolled. The DMC charter will detail the composition, roles and responsibilities and analysis plan for the DMC's activities.

The study may be terminated if unexpected, significant, or unacceptable safety risks to enrolled subjects arise, or if recommended by applicable board(s) after review of safety data.

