## **12.2. Adverse and Serious Adverse Events**

### **12.2.1. Definition of Adverse Events**

#### **12.2.1.1. Adverse Event (AE)**

An AE is any untoward medical occurrence (eg, any unfavorable and unintended sign [including abnormal laboratory findings], symptom or disease) in a clinical investigation subject after providing written informed consent for participation in the study. Therefore, an AE may or may not be temporally or causally associated with the use of a medicinal (investigational) product.

Abnormal laboratory values or test results constitute AEs only if they fulfill at least one of the following criteria:

- they induce clinical signs or symptoms
- they are considered clinically significant
- they require therapy

Clinically significant abnormal laboratory values or test results must be identified through a review of values outside of normal ranges/clinically notable ranges, significant changes from baseline or the previous visit, or values, which are considered non-typical in subjects with the underlying disease.

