## Exceptions to SAE Reporting

Events that are captured as protocol-mandated clinical outcome measures (ie, part of the 8-point NIAID scale) should not be reported as SAEs. This would include initiation of invasive mechanical ventilation and/or ECMO, non-invasive ventilation or high-flow oxygen, and supplemental oxygen. In addition, procedures associated with these clinical outcome measures (eg, intubation or tracheostomy) should not be reported as SAEs. Events that in the judgment of the investigator are clearly a part of the natural history of severe COVID-19 pneumonia with hyper-inflammation should not be reported as SAEs (eg, fever, elevated CRP). All deaths, serious infections and severe granulocytopenia and neutropenia should be reported as SAEs. Per the Investigator Brochure, pneumonia is the only event that is included in the Reference Safety Information (RSI) and would be considered expected or listed. Any other serious related adverse drug reactions would be considered unexpected and would require expedited reporting.

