### **4. GENERAL STATISTICAL CONSIDERATIONS**

Analyses described in this SAP will be conducted separately for each of the two cohorts. Treatment comparison will be primarily between each of the KPL-301 treatment arms (10 mg/kg, 6 mg/kg) vs placebo. Comparisons between the pooled KPL-301 treatment arms vs placebo will also be provided.

Summary statistics for continuous variables will include n (non-missing observations), mean, standard deviation, minimum, median, and maximum. Summary statistics for categorical variables will be presented in terms of frequencies and percentages based on the analysis set unless otherwise specified. In by-visit summary tables, only scheduled visits/timepoints will be summarized.

Time to event data will be summarized using the Kaplan-Meier (KM) method, which will include the estimated median, 25th percentiles, 75th percentiles, and their 95% confidence interval (CI). The CIs will be calculated using a log-log transformation. The event-free probability and its 95% CI will be calculated at days 4, 8, 15, 22, 29, 60 and 90 as appropriate using Greenwood's formula with a log-log transformation.

The 95% confidence interval (CI) of the difference in the proportion (KPL-301 – placebo) will be primary based on Cochran Mantel-Haenszel (CMH) test stratified by the randomization strata for binary (proportion or rate) endpoints.

All relevant subject data will be listed by cohort, treatment, subject and visit/time point including both scheduled and unscheduled visits.

Analyses of selected Day 90 efficacy endpoints will be conducted in the Day 90 analysis set in the Day 29 database lock. All Day 90 efficacy endpoints will be analyzed based on the ITT analysis set at the Day 90 database lock.

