### **4.3. Windowing of Visits**

Data will be summarized by eCRF scheduled visits and allowed visit windows. When there are multiple assessments for a scheduled visit, the first non-missing value will be used. No additional windowing will be considered.

Due to changes of visit windows across protocol versions, the minimum window that can cover windows in all protocol versions will be used in the analysis of the efficacy endpoints: the window is (-2 days, + 2 days) for Day 15 endpoints, (-2 days, + 4 days) for Day 29 endpoints, (-7 days, +14 days) for Day 90 endpoints.

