#### 5.8.1. Adverse Events

An adverse event (AE) is any untoward medical occurrence in a subject or clinical investigation subject administered a pharmaceutical product. An AE does not necessarily have a causal relationship with this treatment. An AE will be defined as treatment-related if its relationship to the study drug is reported as Possibly Related or Definitely Related by Investigator.

An AE is considered treatment-emergent adverse event (TEAE) if the AE begins on/after and within 90 days of the study drug administration. If the date of AE onset is missing or coincides with the date of the study drug administration and AE time is not captured, AE will be considered treatment emergent.

All AEs will be coded using MedDRA version 23.0. A subject experiencing multiple AEs under the same preferred term (PT) or same system organ class (SOC) will be counted only once for that PT or SOC by maximum severity. If a subject experience the same AE more than once with more than one causal relationship to study drug, the strongest causal relationship to study drug will be given precedence. Any missing severity, causality, or outcome will not be imputed and classified as 'Missing'. Detailed imputation rules for missing AE dates are in Section 8.1.1.

An adverse event of special interest (AESI) is one of scientific and medical interest specific to understanding of the Investigational Product and requires close monitoring and rapid communication by the investigator to the sponsor. An AESI may be serious or non-serious.

The number of subjects with at least one TEAE will be tabulated. The following tables summarize incidences of various aspects of TEAEs, treatment-emergent serious AEs (TESAEs), and treatment-emergent AESIs (TEAESIs):

- Overview of TEAEs (summary of all the subsequent items)
- TEAEs by SOC and PT
- TEAEs by PT
- TEAEs by maximum severity (mild, moderate, or severe)
- Drug related TEAEs (related or not related) by SOC and PT
- TESAEs by SOC and PT
- Drug related TESAEs by SOC and PT
- TESAEs by PT
- TEAESIs by SOC and PT
- TEAEs leading to dose interruption by SOC and PT
- TEAEs leading to death by SOC and PT

All information pertaining to adverse events will be listed by subject, detailing verbatim term given by the investigator, preferred term, system organ class, start date, stop date, severity, outcome, action taken and drug relatedness.

Separate listings will be created for Serious TEAEs, and TEAESI, and death.

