### **5.8.2. Clinical Laboratory Parameters**

The following laboratory tests are performed at the Study Site/Clinic laboratories and recorded on the eCRF:

- Screening for tuberculosis
- Pregnancy
- SARS-CoV-2 test with RT-PCR
- Hematology: complete blood count + differential
- Chemistry: electrolytes, blood urea nitrogen, glucose, and CR
- Liver profile: AST, ALT, Alb, AlkP, Tbili, Dbili
- Lipid panel: Cholesterol, total; high-density lipoprotein (HDL) cholesterol; low-density lipoprotein (LDL) cholesterol (calculation); triglycerides; very low-density lipoprotein (VLDL) cholesterol (calculation)
- Urinalysis
- [REDACTED]

The following tests are performed by the central lab:

- Respiratory Viral Panel
- Anti-mavrilimumab Antibody

- [REDACTED]

Continuous laboratory data ([REDACTED], anti-mavrilimumab antibody, hematology, coagulation, chemistry, liver profile, and lipid panel) will be examined for trends using descriptive statistics of actual values and changes from baseline over time by treatment for the safety analysis set.

Shift tables will be produced for hematology and chemistry.

All laboratory results will be presented in by-subject listings.

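### Phase 3 SAP 5.8.2 plans no liver shift table and no by-arm count of subjects meeting the protocol's DILI laboratory criterion

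*Combined protocol and SAP*

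**What the plan says.** Phase 3 SAP 5.8.2 names chemistry (electrolytes, urea nitrogen, glucose, CR) and the liver profile as two separate panels. Continuous laboratory data from both are summarized by arm over time as actual values and changes from baseline. It then plans: "Shift tables will be produced for hematology and chemistry". All results are also listed by subject. SAP 4 includes minimum and maximum in every continuous summary and adds: "In by-visit summary tables, only scheduled visits/timepoints will be summarized". SAP 4.3 adds: "Data will be summarized by eCRF scheduled visits and allowed visit windows", and "When there are multiple assessments for a scheduled visit, the first non-missing value will be used".

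The protocol (12.2.1.3) makes DILI an AESI with numeric limits:

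- With normal liver function at baseline: ALT or AST above 3 x ULN with concurrent bilirubin above 2 x ULN.
- With an abnormal baseline: a doubling of ALT or AST and of bilirubin.
- In both cases no other explanation may exist. Concurrent means the same draw or draws no more than 8 days apart.

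The by-arm route to these events is in SAP 5.8.1: "TEAESIs by SOC and PT". Protocol 12.2.1.1 governs when a laboratory finding becomes an adverse event at all: "Abnormal laboratory values or test results constitute AEs only if they fulfill at least one of the following criteria". The criteria are signs or symptoms, clinical significance, or need for therapy.

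**The concern.** The protocol sets a numeric laboratory limit for liver injury, but no Phase 3 table reports by arm how many subjects crossed it. The only by-arm count depends on an investigator deciding both that the finding is an adverse event and that nothing else explains it. In severe COVID-19 another explanation will often be at hand, so a crossing may properly be left out of the AESI table.

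A count taken from the laboratory data applies one rule to every arm, whatever the presumed cause, and the placebo arm supplies the background rate. That comparison would complement the AESI table. If it is not specified now, it can still be programmed later from the listed data, but it would then not be pre-planned.

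**Working it through.** The plan gives no figure to reproduce, so this is a check of the text with a little counting.

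**1. Is the liver profile covered by the word chemistry?** No. SAP 5.8.2 separates the two in its list of tests and again in its list of continuous data. Protocol Table 4 separates them too. The redactions in SAP 5.8.2 fall in the lists, not in the shift-table sentence. Liver analytes in a shift table: 0 of 6.

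**2. Do the adverse event tables count laboratory crossings?** SAP 5.8.1 lists 11 tables and adds non-serious events: 11 + 1 = 12. All 12 are built from reported events.

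**3. Can the planned liver summaries show the criterion?** They show, by arm and visit, the highest ALT, AST and bilirubin. Suppose that in one arm the maximum ALT is above 3 x ULN and the maximum bilirubin above 2 x ULN. The table reads the same whether one subject holds both values or two subjects hold one each. The criterion concerns one subject, so it cannot be recovered. The abnormal-baseline rule fails in the same way, because it needs a doubling of two analytes in one person. That rule will matter: exclusion criterion 15 admits subjects with ALT or AST up to 10 x ULN.

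**4. Which draws does the 8-day rule need?** Protocol Table 4 schedules post-dose liver tests at Day 3 ± 1, Day 15 ± 2, Day 29 + 4 and Discharge/UNS, with Days 60 and 90 optional. The shortest gaps between the fixed days through Day 29 are:

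- Day 3 to Day 15: (15 − 2) − (3 + 1) = 13 − 4 = 9 days.
- Day 15 to Day 29: 29 − (15 + 2) = 12 days, or 27 − 17 = 10 days with the −2 allowance in SAP 4.3.

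Both exceed 8 days. Through Day 29, two separate draws can therefore satisfy the rule only if at least one is a discharge or other additional draw. Protocol 12.1.5 requires additional results to be recorded, so a count should use them.

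**5. When could the tables be made?** SAP 6 says that only baseline laboratory data are cleaned for the first lock, so they belong at the second.

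**The case against.** The strongest reply is that nothing is lost and much is already covered. Liver values are listed by subject and summarized by arm. A maximum below a limit rules out a crossing among the values summarized, without any judgment of cause. Protocol 12.2.1.1 requires investigators to review out-of-range values and changes from baseline, and 12.2.1.3 asks for prompt work-up of unexplained hepatic abnormalities. AESIs are tabulated and listed. A Data Monitoring Committee will "review unblinded safety data from the Phase 2 and 3 portions of the study"; its charter is not in the documents and may call for such counts. Protocol 13.2.5 promises descriptive safety summaries only, so the SAP breaks no commitment. All of this stands, and it is why the point is minor. None of it is a planned by-arm count of subjects in whom both analytes crossed.

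A reader might infer three stronger things, which the documents do not support:

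- **That neutropenia has the same gap.** The AESI is defined by the number itself, ANC below 1.0 x 10^9/L, with reporting within 24 hours. Protocol 12.5 adds: "All deaths, serious infections and severe granulocytopenia and neutropenia should be reported as SAEs". Hematology includes the differential and has a planned shift table. Only the category boundary is unstated, which is table-shell detail.
- **That the shift tables exclude unscheduled or discharge values.** SAP 4 limits by-visit tables, and no sentence says that shift tables are by visit. The post-baseline value to be used is simply not stated.
- **That the AESI table will undercount DILI.** A crossing with another explanation is not DILI under the protocol. What is missing is the cause-blind laboratory count, and nothing in the documents shows how many crossings would go unreported.

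**Conclusion.** The point holds as a minor gap in the planned tables, not in data collection. No liver analyte has a shift table, none of the 12 adverse event tables is laboratory-derived, and no laboratory table counts subjects meeting the DILI laboratory criterion. The per-analyte summaries cannot substitute for that count. There is no effect on alpha, power or any efficacy result. The number of crossings missing from the AESI table cannot be estimated from the documents and is zero if all are reported. The conclusion rests on reading chemistry as SAP 5.8.2 and Protocol Table 4 define it, and it concerns the SAP tables only.

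**What to change.** Amend Phase 3 SAP 5.8.2, for the safety analysis set at the second database lock, descriptively and by arm:

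- **(a)** Add the liver profile to the shift tables, using the worst post-dose value.
- **(b)** From all post-dose values, including unscheduled and discharge draws, count subjects with ALT or AST above 3 x ULN; with bilirubin above 2 x ULN; with both within 8 days (normal baseline); and with a doubling of ALT or AST and of bilirubin (abnormal baseline). Label these as laboratory criteria irrespective of cause, not as DILI, and place them beside the AESI table.

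State that the visit rules in SAP 4 and 4.3 do not restrict (a) or (b). An ANC category below 1.0 x 10^9/L in the hematology shift table is optional.

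The cost is SAP wording and about two extra tables, with no new samples. Liver tests are run locally, so local ULNs must be in the database or be obtained from sites. The counts will include COVID-related abnormalities in every arm and will exceed true DILI cases. They also cover only sampled days, because telephone visits after discharge have no laboratory tests.

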### 5.8.3. Vital Signs

Vital signs include temperature, respiratory rate, systolic blood pressure/ diastolic blood pressure, and heart rate. Body weight and height will be reported in Body Measurements eCRF.

Actual values of vital signs (including weight) and changes from baseline will be summarized using descriptive statistics by visit.

All vital signs data will be listed.

### 5.8.4. Electrocardiogram (ECG)

All ECG data will be listed.

### 5.8.5. Physical Examination

All physical examination data will be listed.

### 5.8.6. Chest Imaging

Chest imaging data will be listed.

## 6. CHANGES TO PLANNED ANALYSES FROM THE PROTOCOL

- The following other efficacy endpoints are out of scope for this SAP, and will be reported separately
  - [REDACTED]
  - [REDACTED]
  - [REDACTED]
  - [REDACTED]
  - [REDACTED]
  - [REDACTED]
- All randomized subjects will be included in the ITT analysis set.
- Summary of Remdesivir and Corticosteroids Before Day 29 are added
- For favorable Day 29 endpoints, death will be censored at Day 35 instead of Day 30 as specified in the protocol
- The main analyses for the first database lock of Cohort 1 will not use a fixed data cut-off date. Subject level Day 29 dates will be used instead.
  - Efficacy endpoints based on Day 29 will consider data through Day 29 window.
  - Non-efficacy parameters that involve data after Day 29 by definition, e.g., TEAE, CM, will only include data through Day 29 in the first database lock.
  - Lab summary tables will only include baseline; and lab shift tables will not be provided since only baseline lab data will be cleaned in the first DBL.

## 8. APPENDICES

### 8.1. Handling of Missing Safety Data

No imputation will be made for completely missing date unless otherwise specified. General imputation rules mentioned below apply to partially missing or impossible dates:

- If the stop date is not missing, and the imputed start date is after the stop date, the start date will be imputed by the stop date
- If the start date is not missing, and the imputed stop date is before the start date, then the imputed stop date will be equal to the start date
- Any imputed dates need to be logical. For example, last dose date should not be later than death date.

When imputation rules in subsequent sections contradicts the general rule, always follow the general rule.

#### 8.1.1. Adverse Event Date Imputation

Follow the general rule specified in Section 8.1.

##### **Incomplete Start Date:**

*Missing day, month, and year*

No imputation will be made; the corresponding AE will be included.

*Missing day and month*

- If the year is the same as the year of the first dose date, then impute day and month as the day and month of the first dose
- If the year is prior to the year of the first dose date, then impute day and month as 31 Dec
- If the year is after the year of the first dose date, then impute day and month as 01 Jan.

*Missing day only*

- If the month and year are the same as those of the first dose date, then impute day as the day of the first dose date
- If either the year of partial date is before the year of the first dose date, or the years are the same, but the month of partial date is before the month of the first dose date then impute day as last day of the month
- If either the year of partial date is after the year of the first dose date, or the years are the same, but the month of partial date is after the month of the first dose date, then impute day as first day of the month.

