#### **4.1. Randomization, Stratification, and Blinding**

An Interactive Web Response System (IWRS) will be used for assignment of the subject identification number at enrollment, randomization to a treatment arm (10 mg/kg KPL-301, 6 mg/kg KPL-301 or placebo), and assignment of blinded investigational product.

The randomization is stratified by the three following characteristics for subjects in Cohort 1 and by the first two following characteristics for subjects in Cohort 2:

1. Use of approved standard of care antiretroviral therapy: yes vs. no
2. Age: <65 vs.  $\geq 65$  years
3. Acute respiratory distress syndrome (ARDS) status: normal – mild ( $> 200$  PaO2/FiO2) vs. moderate-severe ( $\leq 200$  PaO2/FiO2). If PaO2 is unavailable, use SpO2/FiO2: normal–mild ( $>235$ ) vs. moderate-severe ( $\leq 235$ )

There should be no overlap of subject populations between the two cohorts since Cohort 1 baseline NIAID should be 3 or 4 and Cohort 2 baseline NIAID should be 2. In case of subjects being erroneously randomized under the incorrect cohort, the subjects will be analyzed in the correct cohort defined by the baseline NIAID scale. Subjects with baseline NIAID  $\geq 5$  will be included in Cohort 1 for the ITT and safety populations but excluded from Cohort 1 in the per-protocol analyses.

If subjects were randomized based on incorrect baseline information for use of approved standard of care antiretroviral therapy and age, then the correct strata will be used for stratified analysis rather than the incorrect strata in the IRT.

For ARDS status, data collected in IRT will be used since actual ARDS status at randomization was not collected in EDC. For Cohort 1 subjects who were incorrectly randomized under Cohort 2, the actual ARDS status derived from baseline information in EDC will be used, since the randomization for Cohort 2 is not stratified by ARDS status in the IRT.

If fewer than 5 subjects are in a stratification group of all three (or two for cohort 2) factors, that group will be pooled with another stratification group. If the same situation occurs, strata for the second factor will be pooled. If the same situation still exists, the analysis will be done without stratification.

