## **5.5. Prior and Concomitant Medications**

Prior medications are defined as those taken before the date of the study drug. Concomitant medications are defined as any non-study medication taken during the study i.e., on or after the date of the study drug and within 90 days of the study drug treatment.

The number and percentage of subjects taking prior and concomitant medications will be tabulated separately by anatomical-therapeutic-chemical (ATC) level 2 and preferred drug name by treatment for the safety analysis set. A subject taking the same medication multiple times is counted only once under that preferred drug name. The summary will be sorted in the alphabetic order of ATC classes and preferred terms.

Prior and concomitant medications will be listed with flag.

Medications are coded using the World Health Organization (WHO) Drug dictionary B3 enhanced, version Mar 2020.

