##### *Missing day only*

- If the month and year are the same as those of the last dose date, then impute day as the day of the last dose date
- If either the year of partial date is not the same as the year of the last dose date, or the years are the same, but the month of partial date is not the same as the month of the last dose date, then impute day as last day of the month.

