#### **8.1.2. Concomitant Medication Date Imputation**

Follow the general rules specified in Section [8.1](#) and Section [8.1.1](#).

Signature Page for RIM-CLIN-000916 v5.0

Approval	
----------	--

Approval	
----------	--

Approval	
----------	--

Approval	
----------	--

Signature Page for RIM-CLIN-000916 v5.0

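### Phase 3 SAP 8.1.2 reuses the adverse-event partial-date rule for medications, so a drug with a missing start day in the dosing month and no recorded stop before dosing loses its prior status

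*Combined protocol and SAP*

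**What the plan says.** Phase 3 SAP 8.1.2 (Concomitant Medication Date Imputation) reads "Follow the general rules specified in Section" 8.1 and 8.1.1, and adds nothing specific to medications. Section 8.1.1 is the adverse-event rule. Its parts that matter here are:

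- Start day missing, dosing month: "If the month and year are the same as those of the first dose date, then impute day as the day of the first dose" (that is, the dosing date).
- Start day and month missing, dosing year: "then impute day and month as the day and month of the first dose".
- Start day missing, earlier month: where the "month of partial date is before the month of the first dose date then impute day as last day of the month".
- Stop day missing, dosing month: "If the month and year are the same as those of the last dose date, then impute day as the day of the last dose". With a single infusion, the first and last dose dates are the same day.

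Section 8.1 adds a general rule that takes precedence: when the stop date is known and the imputed start falls after it, the start is set to the stop date.

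Section 5.5 then classifies the drugs: "Prior medications are defined as those taken before the date of the study drug". Concomitant drugs are those taken "on or after the date of the study drug and within 90 days of the study drug treatment". The two are tabulated separately on the safety analysis set and flagged in a listing. The Phase 2 SAP has the same date rules.

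**The concern.** Moving an uncertain start onto the dosing day is the cautious choice for an adverse event, because it makes the event treatment-emergent. For a medication it works the other way and removes exposure that came before dosing. The drugs most exposed are antivirals and corticosteroids begun in the same admission and still running at infusion. Their start usually falls in the dosing month, and there is no earlier stop date to rescue them.

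A second case is worse. If a course began and ended before dosing in the dosing month and both days are missing, start and stop are both set to the dosing day. The drug then appears as a one-day concomitant medication on Day 1 and not as a prior one, which is the opposite of what happened.

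At stake is how well the prior-medication table and listing describe treatment before the infusion.

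**Working it through.** The plan gives no figure of its own on this point, so there is none to reproduce. The check applies the rules to known dates and then counts calendar days.

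**Examples, dosing on 20 March 2021**

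| True course | What is missing | Imputed | Status under 5.5 |
|---|---|---|---|
| 15 March, ongoing | start day | start 20 March | not prior (wrong) |
| 10 to 14 March | both days | start and stop 20 March | concomitant only (wrong) |
| 10 March to a known stop on 14 March | start day | 20 March, pulled back to 14 March by 8.1 | prior (right) |
| 25 February, ongoing | start day | 28 February | prior (right) |

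In the second row the imputed start equals the imputed stop, so the general rule in 8.1 is not triggered.

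**How often the start shares the dosing month**

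Assumptions: dosing dates are uniform over the 365 days of 2021; the true start is uniform over the look-back; the start day is missing but month and year are known; and no stop before dosing is recorded. The 7-day look-back comes from protocol 7.2, exclusion 2, which bars subjects hospitalized for more than 7 days before randomization.

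For a start k days before dosing, the start falls in the previous month only when dosing is on one of the first k days of a month. Over 12 months that is 12k days, so the share in the dosing month is 1 - 12k/365. Averaging over the look-back:

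- 1-3 days (mean k = 2): 1 - 24/365 = 93.4%
- 1-7 days (mean k = 4): 1 - 48/365 = 86.8%
- 1-14 days (mean k = 7.5): 1 - 90/365 = 75.3%
- 1-56 days, the 8-week biologic washout: 26.3%, by enumerating all dates

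With a known stop before dosing, the loss is 0% for every look-back.

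The protocol's Schedule of Activities (footnote 10) allows up to 24 hours from randomization to dosing. Extending the look-back to 1-8 days changes little: 1 - 54/365 = 85.2%.

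**Share of all such records**

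The proportion of partial start dates is not given. If it were 2% to 10% (an assumption), the records affected among drugs started 1-7 days before dosing with no pre-dosing stop would be 0.868 x 2% = 1.7% to 0.868 x 10% = 8.7%. These are shares of records. A user of a drug is missed only if every pre-dosing record of that drug is affected.

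**The case against.** The strongest reply is that this changes a label in a descriptive table and nothing more. A drug that continues past dosing is still counted, correctly, as concomitant. Baseline antiviral use is tabulated separately by IWRS stratum and by actual stratum (Phase 3 SAP 5.3.2). Section 6 adds a summary of remdesivir and corticosteroids before Day 29, which a drug moved to Day 1 still enters. Protocol 8.2 asks for the time, dose and duration of COVID-19 therapies, so missing start days for these drugs should be uncommon. All of this stands, and it keeps the point minor. It does not make the classification right.

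Three stronger readings are tempting, and the documents do not support them:

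- *The primary tests are affected.* Section 4.1 says that where baseline antiviral use or age was entered wrongly, "then the correct strata will be used for stratified analysis rather than the incorrect strata in the IRT". A reader might infer that a remdesivir user with a partial start date becomes a non-user in the CMH and log-rank strata. Section 4.1 keeps the IRT value for ARDS because actual status was not collected in EDC, which hints that the antiviral correction comes from EDC data. Nothing says that imputed medication dates are used, and section 4.4 assigns the 8.1 rules to safety data.
- *The per-protocol set is affected through drugs barred by exclusion 6.* Sections 3.3 and 4.5 base that set on blinded review of protocol deviations and an evaluability document, not on a prior flag.
- *Every drug with a missing start day is affected, prohibited biologics included.* Earlier-month starts and known pre-dosing stops are protected, and only about 26% of starts within the 8-week window share the dosing month.

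**Conclusion.** The point holds in a limited form and is minor. A drug begun before dosing loses prior status when its start day is missing in the dosing month, or its start is year-only in the dosing year, and no stop before dosing is recorded. If the stop day is also missing in that month, a course that ended before dosing becomes a one-day drug on Day 1.

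For starts 1-7 days before dosing, about 87% of records with a missing start day and no recorded pre-dosing stop are misclassified. That figure rests on uniform dosing dates and start lags. How many records have partial dates is unknown. The effect shown is confined to the 5.5 tabulation and listing flags. An effect on the antiviral stratum, the primary tests or the per-protocol set is possible, but the documents do not state one.

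**What to change.** In the Phase 3 SAP, give 8.1.2 its own rule:

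- Impute a partial start to the earliest date compatible with the known parts (first of the month, or 01 Jan).
- Impute a partial stop to the latest compatible date (month end, or 31 Dec), capped at death or last contact.
- Keep both subject to the general rules in 8.1, and derive the prior and concomitant flags from the results.
- As a safeguard, state that imputed medication dates are not used to override the IRT antiviral stratum in 4.1.

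Under first-of-month imputation, 0% of drugs started 1-7 days before dosing lose prior status. A finished course with its stop day missing in the dosing month would generally still be flagged as concomitant, but it would now be flagged as prior too.

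The cost is a few lines of SAP text and a small programming change. The downside is a mirror error: some drugs started after dosing in the dosing month with a missing day will also be flagged as prior. Under the same assumptions, for starts 1-7 days after dosing, 317/365 fall in the dosing month. Dosing on the first of a month (12/365) does no harm, so 305/365 = 83.6% of those with a missing start day would gain the extra flag. They keep their concomitant flag, so no true status is lost.
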